**Listing 16.2.4.3**  
**Concomitant Medications [1]**

Group	Subject ID	Medication	Standardized Medication Name [2]	Indication	Start Date	Stop Date	Period[3]	Dose	Unit	Route	Frequency
Sentinel	302-XX-XXX	XXXXXXX	XXXXXXX	XXXXXXX	YYYY-MM-DD	YYYY-MM-DD Or ONGOING	Inf 15m/ Inf 10m/	XXXX	XXXX	XXXX	XX
Core HIV-infected	302-XX-XXX	XXXXXXX	XXXXXXX	XXXXXXX	YYYY-MM-DD	YYYY-MM-DD Or ONGOING	Push 30s/ Screening	XXXX	XXXX	XXXX	XX
Core HIV-uninfected	302-XX-XXX	XXXXXXX	XXXXXXX	XXXXXXX	YYYY-MM-DD	YYYY-MM-DD Or ONGOING	Push 30s/ Screening	XXXX	XXXX	XXXX	XX

[1] Medications taken on or after Screening visit.

[2] Medications were coded with WHO Drug Dictionary Version March, 2019.

[3] Period represents the timeframe when the medication was STARTED.

**Listing 16.2.4.4**  
**Concomitant Procedures [1]**

Group	Subject ID	Procedure	Procedure Date	Period[2]	Reason
Sentinel	302-XX-XXX	XXXXXXXX	YYYY-MM-DD	Inf 15m/ Inf 10m/ Bolus 5m/	XXXXXXXX: specify
Core HIV-infected	302-XX-XXX	XXXXXXXX	YYYY-MM-DD	Inf 15m/ Inf 10m/ Bolus 5m/	XXXXXXXX
Core HIV-uninfected	302-XX-XXX	XXXXXXXX	YYYY-MM-DD	Bolus 1m/ Push 30s/ Screening	XXXXXXXX

[1] Procedures occurring on or after the Day 1 visit.

[2] Period represents the timeframe when the procedure took place.

Westat (Created on DDMMYYYY)  
S:\TMB302\DA\SAS\L\_CONPROCS.SAS

**Listing 16.2.5.1**  
**Post-Administration Observation**

Group	Subject ID	Visit	Visit Date	Observed After Study Drug	Start Time of Observation (hh:mm)	End Time of Observation (hh:mm)	Comments
Sentinel	302-XX-XXX	XXX	YYYY-MM-DD	YES	XX:XX	XX:XX	XXXXXXXXXXXXXXXXXXXX
Core HIV-infected	302-XX-XXX	XXX	YYYY-MM-DD	NO	XX:XX	XX:XX	XXXXXXXXXXXXXXXXXXXX
Core HIV-uninfected	302-XX-XXX	XXX	YYYY-MM-DD	NO	XX:XX	XX:XX	XXXXXXXXXXXXXXXXXXXX

Westat (Created on DDMMMYYYY)  
S:\TMB302\DA\SAS\L\_POSTINJECT.SAS

**Listing 16.2.5.2**  
**PK Results**

Group	Subject ID	Visit	Visit Date (Study Day)	Period [1]	Scheduled Time point	Time of Collection (hh:mm)	Concentration (ng/mL) [2]	AUC (day*ug/mL) [3]
Sentinel	302-XX-XXX	XXX	YYYY-MM-DD (xx)	XXX	XXX	XX:XX	xxx	xxx
Core HIV-infected	302-XX-XXX	XXX	YYYY-MM-DD (xx)	XXX	XXX	XX:XX	xxx*	xxx
Core HIV-uninfected	302-XX-XXX	XXX	YYYY-MM-DD (xx)	XXX	XXX	XX:XX	xxx	xxx

[1] Period represents the timeframe when the visit took place. NOTE - When labs are assessed pre-dose, the value of PERIOD in the lab listings will be previous to the value of PERIOD in listings for post-dose assessments.

[2] \*Indicates TROUGH value.

[3] AUC calculated for Day 1 to Day 15, Day 15 to 29, Day 71 to Day 85, Day 85 to Day 99 (Sentinel Group) and Day 1 to Day 15, Day 15 to 29, Day 43 to Day 57, Day 71 to Day 85 (Core Groups).

Westat (Created on DDMMYYYY)  
S:\TMB302\DA\SAS\L\_PK.SAS

**Listing 16.2.6.1**  
**Treatment Emergent Adverse Events [1]**

Group	Subject ID	System Organ Class	Preferred Term [2]	Adverse Event Verbatim	Start Date (Study Day)	Stop Date (Study Day)	Period [3]	Sev. / Grade [4]	SAE	Caus. [5]	Action Taken [6]	Outcm. [7]	CDC AIDS-Defining Cond.
Sentinel	302-XX-XXX	MUSCULOSKELETAL AND CONNECTIVE TISSUE	ARTHRALGIA	MILD PAIN (DUE TO FALL AT	20160923 (283)	20161010 (300)	Inf15m	1	N	0	0	1	N
Core HIV-infected	302-XX-XXX	NERVOUS SYSTEM DISORDERS INVESTIGATIONS	HEADACHE BREATH SOUNDS ABNORMAL	WORSENING HEADACHES DECREASED BREATH SOUNDS	20160516 (3)	20160524 (11)	Bolus1m	2	Y	4	4	1	N
Core HIV-uninfected	302-XX-XXX	NERVOUS SYSTEM DISORDERS INVESTIGATIONS	HEADACHE BREATH SOUNDS ABNORMAL	WORSENING HEADACHES DECREASED BREATH SOUNDS	20160516 (7)	20160524 (27)	Push30s	1	N	0	0	1	N

[1] Adverse events occurring on or after the Day 1 visit.

[2] Adverse events are coded using MedDRA Version 22.0.

[3] Period represents the timeframe when the adverse event STARTED.

[4] Severity/Grade: 1=Mild, 2=Moderate, 3=Severe, 4=Potentially Life Threatening, 5=Death.

[5] Causality: 0=Unrelated, 1=Possible, 2=Probable, 3=Definite.

[6] Action Taken: 0=None, 1=Medication Given, 2=Non-Medication Therapy, 3=Suspended Study Drug, 4=Permanently Discontinued Study Drug, 99=Other.

[7] Outcome: 1=Resolved, 2=Resolved w/sequelae, 3=Ongoing, 4=Worsened, 5=Death, 7=Chronic/Stable, 98=Unknown.

Westat (Created on DDMMMYYYY)  
S:\TMB302\DA\SAS\L\_AE.SAS

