#### **HIV-uninfected individuals:**

**Pre-Steady-State Phase:** Subjects will receive a 2000 mg infusion of Trogarzo® over 60 minutes on Day -55 followed by 3 doses of 800 mg infusion over 15 minutes on Days -41, -27, and -13. On Day 1 the subjects will enter the Study Treatment Phase.

**Study Treatment Phase:** These HIV-uninfected subjects will receive an 800 mg dose of Trogarzo® in accordance with the prescribing information (diluted in 250 mL normal saline and administered over 15 minutes via IVI) at Day 1/Baseline and again at Day 15. Every 2 weeks thereafter through Day 71 (10 weeks), subsequent doses will be administered via undiluted IV push over 30 seconds. After the Day 71 IV push dose, HIV-uninfected Core Group subjects discontinue Trogarzo® therapy.

Pharmacokinetic samples will be collected in the study to evaluate serum concentrations and the PK profile of Trogarzo®. In particular, data will be collected to compare serum drug concentrations (AUC and trough) after IVI of the 800 mg diluted drug over 15 minutes to IV push of the undiluted drug over 30 seconds. Pre-dose samples will be collected at selected timepoints, along with samples at 1, 24, and 72 hours post-dose, and 7 and 14 days post-dose for the first two doses of study drug (via IVI) for HIV-infected participants and after steady state is achieved in HIV-uninfected healthy volunteers, and for all 30-second IV push doses for all subjects in the Sentinel and Core Groups (see [Table 1](#), [Table 2](#), and [Table 3](#) for sample collection timepoints). Samples collected at the 24- and 72-hour post-dose timepoints, and those collected at the 7-day post-dose timepoints when a study visit is not otherwise already scheduled will require additional visits for PK sample collection only.

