**Listing 16.2.7.1**  
**Treatment Emergent Adverse Events [1]**

Group	Subject ID	System Organ Class	Preferred Term [2]	Adverse Event Verbatim			Start Date (Study Day)	Stop Date (Study Day)	Period [3]	Grade [4]	Sev./ SAE	Action Taken [5]	Caus. [6]	Action Taken [7]	Outcm. [8]	CDC AIDS-Defining Cond. [9]
				XXXXXXX	YYYY-MM-DD (XX)	YYYY-MM-DD (XX)										
IM HIV-infected	XX-XXX	XXXXXXXXXXXX	XXXXXXXXXX	XXXXXXXXXX	YYYY-MM-DD (XX)	YYYY-MM-DD (XX)	XXXX	X	N/Y		X	X	X	X	X	X
IM HIV-uninfected	XX-XXX	XXXXXXXXXXXX	XXXXXXXXXX	XXXXXXXXXX	YYYY-MM-DD (XX)	YYYY-MM-DD (XX)	XXXX	X	N/Y		X	X	X	X	X	X
		XXXXXXXXXXXX	XXXXXXXXXX	XXXXXXXXXX	YYYY-MM-DD (XX)	YYYY-MM-DD (XX)	XXXX	X	N/Y		X	X	X	X	X	X

[1] Adverse events occurring on or after the date of first dose of study medication.

[2] Adverse events are coded using MedDRA Version 22.0.

[3] Period represents the timeframe when the adverse event STARTED.

[4] Severity/Grade: 1=Mild, 2=Moderate, 3=Severe, 4=Potentially Life Threatening, 5=Death.

[5] Causality: 0=Unrelated, 4=Suspected Adverse Reaction.

[6] Action Taken: 0=None, 1=Medication Given, 2=Non-Medication Therapy, 3=Suspended Study Drug, 4=Permanently Discontinued Study Drug, 99=Other.

[7] Outcome: 1=Resolved, 2=Resolved w/sequelae, 3=Ongoing, 4=Worsened, 5=Death, 7=Chronic/Stable, 98=Unknown.

*Notes to programmer: Confirm that footnotes match final version of CRF and coding used in data.*

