- Day 43 (6 weeks): 800 mg undiluted (at 150 mg/mL) via IV push over 30 seconds
- Day 57 (8 weeks): 800 mg undiluted (at 150 mg/mL) via IV push over 30 seconds
- Day 71 (10 weeks): 800 mg undiluted (at 150 mg/mL) via IV push over 30 seconds
- Day 85 (12 weeks), EOS visit: 800 mg diluted in 250 mL normal saline (at 3.2 mg/mL) via IV Infusion over 15 minutes per approved Trogarzo® prescribing information

Core Group: HIV-uninfected subjects

**Pre-Steady State Phase:** Subjects will receive a 2000 mg infusion over 60 minutes on Day minus 55 followed by 3 doses of 800 mg infusion over 15 minutes on Days minus 41, 27, and Day minus 13. On Day 1 the subjects will enter the Study Treatment Phase.

**Study Treatment Phase:** These HIV-uninfected subjects will receive an 800 mg dose of Trogarzo® in accordance with the prescribing information (diluted in 250 mL normal saline and administered over 15 minutes via IV infusion) at Day 1/Baseline and again at Day 15. Every two weeks thereafter through Day 71 (10 weeks), subsequent doses will be administered via undiluted IV Push over 30 seconds. After the Day 71 infusion, HIV-uninfected Core Group subjects discontinue Trogarzo® infusion therapy.

All HIV-infected study subjects in both Groups will be observed for 15 minutes after each study drug administration, and HIV-uninfected subjects will be observed for 60 minutes. All adverse events (AEs) will be recorded. Vital signs will be measured and recorded at the beginning and end of this observation period.

PK samples will be collected during the study to evaluate serum concentrations and the PK profile of Trogarzo®. In particular, data will be collected to compare serum drug concentrations (AUC and trough) after IV infusion of the 800 mg diluted drug over 15 minutes to IV push of the undiluted drug over 30 seconds. Pre-dose samples will be collected at selected time points, along with samples at 1, 24, and 72 hours post-dose, and 7 and 14 days post-dose for the first two doses of study drug (via IV Infusion) for HIV-infected participants and after steady state is achieved in HIV-uninfected healthy volunteers, and for all, of the 30-second IV push doses for all subjects in both Groups. Samples collected at 24 and 72 hour post-dose time points, and those collected at 7-day post-dose time points when a study visit is not otherwise already scheduled will require additional visits for PK sample collection only.

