### **3.3.3. Baseline Values**

Baseline is defined as the last assessment prior to the first dose of study drug (Day 1 for all HIV infected subjects, Day -55 for HIV uninfected subjects).

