##### **4.3.2. AEs**

All AEs will be coded using MedDRA dictionary version 22.0. The use of another version will not be considered a violation of the SAP, nor require an amendment to the plan. All summary tables will be based on coded preferred terms (PTs), instead of verbatim terms. The categories and definitions of severity and causal relationship for all AEs, including the criteria for which an AE is to be classified as “serious,” are as described in the protocol (Section 8).

A treatment-emergent AE (TEAE) is defined as any event not present before exposure to study drug or any event already present that worsens in either intensity or frequency following exposure to study drug. All AEs entered on the Adverse Events eCRF will be analyzed as TEAEs. A TEAE with missing severity or relationship will be considered severe or related, respectively.

The overall incidence of TEAEs will be summarized for all subjects in the SAF Population. The number and percentage of subjects having the following will be tabulated:

- TEAE
- Serious TEAE
- TEAE leading to discontinuation
- TEAE with outcome of death

- TEAE related to study drug (definitely, probably, or possibly)
- Severe TEAE
- Class C TEAE per the Centers for Disease Control and Prevention (CDC) Classification System for HIV Infection

The overall incidence of TEAEs will also be summarized by System Organ Class (SOC), and by SOC and PT. The number and percentage of subjects reporting an event, as well as the number of events reported by the subjects will be tabulated. The incidence of serious TEAEs and TEAEs leading to study discontinuation (if any) will be summarized in the same manner. If there are multiple occurrences of the same TEAE within any SOC or PT for the same subject, only the first occurrence will be counted.

The incidence of TEAEs by severity/grade (mild, moderate, severe, or potentially life-threatening) and by relationship to study drug (unrelated, possibly related, probably related, and definitely related), and the incidence of serious AEs (SAEs) by relationship to study drug, will also be summarized.

All other AEs will be classified as non-TEAEs and identified in listings only. Serious TEAEs, TEAEs leading to study discontinuation, and TEAEs with an outcome of death will be presented in separate listings, if needed.

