**Table 14.3.1.1.3**  
**Treatment-Emergent Adverse Events Summary**  
**Safety Population - Core HIV-uninfected Group**

	Core HIV-uninfected Group (N=XX)			
	Pre-Steady State + IV Infusions Period	Investigational Period 30 sec IV Pushes	Follow-up Period	Total
TEAE [1]	n (xxx.x%)	n (xxx.x%)	n (xxx.x%)	n (xxx.x%)
Serious TEAE [2]	n (xxx.x%)	n (xxx.x%)	n (xxx.x%)	n (xxx.x%)
TEAE with Death Outcome	n (xxx.x%)	n (xxx.x%)	n (xxx.x%)	n (xxx.x%)
TEAE Leading to Discontinuation	n (xxx.x%)	n (xxx.x%)	n (xxx.x%)	n (xxx.x%)
TEAE Related to Study Drug [3]	n (xxx.x%)	n (xxx.x%)	n (xxx.x%)	n (xxx.x%)
Severe TEAE [4]	n (xxx.x%)	n (xxx.x%)	n (xxx.x%)	n (xxx.x%)
Class C TEAE [5]	n (xxx.x%)	n (xxx.x%)	n (xxx.x%)	n (xxx.x%)

N = All subjects in the Safety Population (displayed according to actual treatment received), and denominator for percentage calculations.

TEAE = Treatment-Emergent Adverse Event.

NOTE: Identical TEAEs are counted only once per subject.

[1] Number(%) of subjects with at least one TEAE.

[2] Number(%) of subjects with at least one serious TEAE, excluding death, as identified by the investigator.

[3] Definitely, probably, or possibly.

[4] Severity/Grade 3 or higher (severe or potentially life threatening).

[5] Per the CDC Classification System for HIV Infection.

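### The Day 1 cut-off in the three IV push adverse event listings contradicts the SAP's own TEAE definition and, applied literally, omits events from the pre-steady-state phase in uninfected Core volunteers

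*SAP*

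**What the plan says.** The SAP file holds two plans, one for the IV push portion and one for the IM portion. This point concerns the IV push plan.

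- **Listing footnotes.** In IV push Listings 16.2.6.1, 16.2.6.2 and 16.2.6.3, footnote [1] is attached to the treatment-emergent term in the title and reads "Adverse events occurring on or after the Day 1 visit". One footnote serves every group, and each mock has rows for Core HIV-uninfected subjects.
- **Dosing of uninfected Core volunteers.** IV push SAP 2.1 states: "Subjects will receive a 2000 mg infusion over 60 minutes on Day minus 55". Protocol 3.1 gives the remaining pre-steady-state doses: "followed by 3 doses of 800 mg infusion over 15 minutes on Days -41, -27, and -13". Protocol Table 2 labels all four administrations as study drug.
- **TEAE definition.** IV push SAP 4.3.2: "A treatment-emergent AE (TEAE) is defined as any event not present before exposure to study drug", or an existing event that worsens after exposure. The same paragraph adds: "All AEs entered on the Adverse Events eCRF will be analyzed as TEAEs".
- **Baseline.** IV push SAP 3.3.3 takes the last assessment before the first dose, specified as "Day -55 for HIV uninfected subjects".
- **Tables.** IV push mock Table 14.3.1.1.3, the TEAE summary for this group, has a column headed "Pre-Steady State + IV Infusions Period". Tables 14.3.1.2.3, 14.3.1.3.3 and 14.3.1.4.3 carry the same period.
- **IM counterpart.** Footnote [1] in IM Listings 16.2.7.1 to 16.2.7.3 reads "Adverse events occurring on or after the date of first dose of study medication".

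**The concern.** For Sentinel and HIV-infected Core subjects, the first study dose is given on Day 1, so a Day 1 cut-off and a first-dose cut-off select the same events. For uninfected Core volunteers they differ by the whole pre-steady-state phase, which includes the first exposure of drug-naive healthy people and the 2000 mg load.

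That phase can produce events a reader would want to trace. Under Protocol 4.3, a dose-limiting toxicity in an uninfected Core volunteer counts if it follows an infusion as well as a push, and the volunteer then stops dosing. Protocol 4.4 counts such events toward ending volunteer enrollment. A volunteer who stops after a pre-steady-state dose may never have a Day 1 visit, yet belongs to the Safety Population, which requires only one partial dose.

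If the footnote were programmed as written, that volunteer's event would be counted in the tables but absent from the TEAE listing, the serious TEAE listing and the discontinuation/death listing. No other AE listing would pick it up. SAP 4.3.2 sends events that are not TEAEs to listings only, but the IV push listing contents include no listing for them.

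**Working it through.** The plan states no figure here to reproduce. The check compares the texts and counts the affected exposure.

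**1. Which date anchors treatment emergence for an uninfected Core volunteer?**

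| Place in the documents | Anchor |
|---|---|
| IV push SAP 4.3.2 | Exposure to study drug, so Day -55 |
| IV push SAP 3.3.3 | First dose, given as Day -55 |
| IV push Tables 14.3.1.1.3, 14.3.1.2.3, 14.3.1.3.3, 14.3.1.4.3 | Pre-steady-state period included, so Day -55 |
| IM Listings 16.2.7.1 to 16.2.7.3 | Date of first dose |
| IV push Listings 16.2.6.1 to 16.2.6.3 | Day 1 visit |

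Only the last row departs from the others.

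**2. How much exposure lies before Day 1?** Inputs are the dosing days in Protocol 3.1 and IV push SAP 2.1, and the Day 99 end-of-study visit.

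- Doses: Days -55, -41, -27 and -13 before Day 1; Days 1, 15, 29, 43, 57 and 71 from Day 1 on. Share before Day 1 = 4 / (4 + 6) = 4/10 = 40%.
- Amount: before Day 1, 2000 + 3 × 800 = 4400 mg. In total, 2000 + 9 × 800 = 9200 mg. Share = 4400 / 9200 = 47.8%.
- Time: Day -55 to Day 1 is 1 − (−55) = 56 days. Day -55 to Day 99 is 99 − (−55) = 154 days. Share = 56 / 154 = 36.4%. The 14-day step from Day -13 to Day 1 confirms this day count.

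**3. Which events are affected?** IV push SAP 3.4.1 assigns AEs to periods by start date. On that basis, the footnote excludes events with onset from Day -55 up to Day 1. With a first-dose anchor, the listing window gains those 56 days and 4 administrations per uninfected Core subject and does not change for anyone else.

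**The case against.** The strongest reply is that the governing text is already right. SAP 4.3.2 anchors TEAEs on exposure and treats every AE on the eCRF as a TEAE, so under that rule nothing is excluded. The footnote is a caption on a mock shell, and the shells are visibly carried over from other work: example dates in 2016, bolus periods shown for Core subjects who receive no bolus, and a causality code of 4 where the key runs from 0 to 3. The programming notes ask for all applicable data in each listing and for footnotes to be confirmed against the CRF and coding.

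Much of this stands. It shows that the footnote is probably a leftover rather than a decision, and that events are lost only if the program follows it. It does not remove the contradiction. The note on applicable data concerns treatment groups only partly displayed in the mocks, and the note on footnotes concerns the CRF and coding. Neither addresses the analysis window. If the program ignores the footnote, the final listing carries a false definition; if it follows the footnote, listings and tables disagree.

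Three stronger readings are tempting, and the documents do not support them.

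- *Pre-Day 1 events drop out of the safety analysis.* They do not. The summary tables for this group include the period.
- *Narratives or SAE documentation would be missing.* These are line listings, and neither document says narratives are built from them. AE reporting runs from consent (Protocol 8.3), SAEs go through their own report form with source records (8.6), and SAEs and Grade 3 and 4 AEs are forwarded to the DMC (8.8). Listing 16.2.1.2 would still show discontinuation reasons and death dates, though not AE detail.
- *About a third of the safety data is at risk.* The 36% is follow-up time per uninfected Core subject, not a share of events. Neither document says how many of the 15 Core subjects will be uninfected, so the study-level effect cannot be sized.

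**Conclusion.** The inconsistency is real and limited. Footnote [1] in three IV push listings contradicts SAP 4.3.2, SAP 3.3.3 and the tables for the same group. Applied literally, it would remove from the subject-level AE, SAE and discontinuation/death listings any event starting in the 56 days and 4 of 10 doses before Day 1 in HIV-uninfected Core volunteers, and those listings would not reconcile with the summary tables.

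This rests on two assumptions: that the program applies the footnote as a selection rule, and that event timing is judged by start date. No test, denominator or pharmacokinetic comparison changes. It is a correction to the listing specification rather than to the analysis. It is worth making because safety is a primary objective and the events concerned occur in healthy volunteers at first exposure.

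**What to change.** In IV push Listings 16.2.6.1, 16.2.6.2 and 16.2.6.3, replace footnote [1] with the wording the sponsor already uses in the IM listings: "Adverse events occurring on or after the date of first dose of study medication". Adding in brackets that this is Day 1 for HIV-infected subjects and Day -55 for HIV-uninfected subjects would remove any doubt. The listing programs should select events on the same date, and the listed events for uninfected Core subjects should be checked against the counts in Tables 14.3.1.1.3 to 14.3.1.4.3.

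The cost is one footnote in three shells and, if the cut-off was programmed, one date condition. No data collection, design element or statistical test is affected.

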**Notes to programmer: Confirm that footnotes match final version of CRF and coding used in data.**

**Listing 16.2.6.2**  
**Treatment Emergent Serious Adverse Events [1]**

Group	Subject ID	System Organ Class	Preferred Term [2]	Adverse Event Verbatim	Start Date (Study Day)	Stop Date (Study Day)	Sev. / Period [3]	Grade [4]	Caus. [5]	Action Taken [6]	Outcm. [7]	CDC AIDS-Defining Cond.
Sentinel	302-XX-XXX	MUSCULOSKELETAL AND CONNECTIVE TISSUE	ARTHRALGIA	MILD PAIN (DUE TO FALL AT	20160923 (283)	20161010 (300)	Inf15m	1	0	0	1	N
Core HIV-infected	302-XX-XXX	NERVOUS SYSTEM DISORDERS INVESTIGATIONS	HEADACHE BREATH SOUNDS ABNORMAL	WORSENING HEADACHES DECREASED BREATH SOUNDS	20160516 (3)	20160524 (11)	Bolus1m	2	4	4	1	N
Core HIV-uninfected	302-XX-XXX	NERVOUS SYSTEM DISORDERS INVESTIGATIONS	HEADACHE BREATH SOUNDS ABNORMAL	WORSENING HEADACHES DECREASED BREATH SOUNDS	20160516 (7)	20160609 (27)	Push30s	1	0	0	1	N

[1] Adverse events occurring on or after the Day 1 visit.

[2] Adverse events are coded using MedDRA Version 22.0.

[3] Period represents the timeframe when the adverse event STARTED.

[4] Severity/Grade: 1=Mild, 2=Moderate, 3=Severe, 4=Potentially Life Threatening, 5=Death.

[5] Causality: 0=Unrelated, 1=Possible, 2=Probable, 3=Definite.

[6] Action Taken: 0=None, 1=Medication Given, 2=Non-Medication Therapy, 3=Suspended Study Drug, 4=Permanently Discontinued Study Drug, 99=Other.

[7] Outcome: 1=Resolved, 2=Resolved w/sequelae, 3=Ongoing, 4=Worsened, 5=Death, 7=Chronic/Stable, 98=Unknown.

Westat (Created on DDMMYYYY)

S:\TMB302\DA\SAS\L SAE.SAS

**Listing 16.2.6.3**  
**Treatment Emergent Adverse Events [1] Leading to Study Discontinuation or Death**

Group	Subject ID	System Organ Class	Preferred Term [2]	Adverse Event Verbatim	Start Date (Study Day)	Stop Date (Study Day)	Period [3]	Sev. / Grade [4]	SAE	Caus. [5]	Action Taken [6]	Outcm. [7]	CDC AIDS-Defining Cond.
Sentinel	302-XX-XXX	MUSCULOSKELETAL AND CONNECTIVE TISSUE	ARTHRALGIA	MILD PAIN (DUE TO FALL AT	20160923 (283)	20161010 (300)	Inf15m	1	N	0	0	1	N
Core HIV-infected	302-XX-XXX	NERVOUS SYSTEM DISORDERS INVESTIGATIONS	HEADACHE BREATH SOUNDS ABNORMAL	WORSENING HEADACHES DECREASED BREATH SOUNDS	20160516 (3)	20160524 (11)	Bolus1m	2	Y	4	4	1	N
Core HIV-uninfected	302-XX-XXX	NERVOUS SYSTEM DISORDERS INVESTIGATIONS	HEADACHE BREATH SOUNDS ABNORMAL	WORSENING HEADACHES DECREASED BREATH SOUNDS	20160516 (7)	20160524 (11)	Bolus1m	2	Y	4	4	1	N
					20160520 (7)	20160609 (27)	Push30s	1	N	0	0	1	N

[1] Adverse events occurring on or after the Day 1 visit.

[2] Adverse events are coded using MedDRA Version 22.0.

[3] Period represents the timeframe when the adverse event STARTED.

[4] Severity/Grade: 1=Mild, 2=Moderate, 3=Severe, 4=Potentially Life Threatening, 5=Death.

[5] Causality: 0=Unrelated, 1=Possible, 2=Probable, 3=Definite.

[6] Action Taken: 0=None, 1=Medication Given, 2=Non-Medication Therapy, 3=Suspended Study Drug, 4=Permanently Discontinued Study Drug, 99=Other.

[7] Outcome: 1=Resolved, 2=Resolved w/sequelae, 3=Ongoing, 4=Worsened, 5=Death, 7=Chronic/Stable, 98=Unknown.

Westat (Created on DDMMYYYY)  
S:\TMB302\DA\SAS\L AEDISC.SAS

